16.5. Treatment Adherence Questionnaire – Baseline

Below are some questions regarding your use of your previous MS therapy prior to Plegridy. Please answer these questions as best as you can in reference to the last 28 days on your previous treatment

You can also seek help from a caregiver (anyone who usually provides care to you at home) to answer these questions.

1. During the last 28 days on your prior treatment, did you take all of your recommended doses of your MS treatment? Yes No

2. List all the reasons for not taking entire recommended dose. Please check the responses that apply.
 - Injection Anxiety
 - Skin Reaction
 - Forgot to take
 - Financial (I could not afford my medication)
 - Pain at injection site
 - Depression
 - Headache
 - Fatigue
 - Weakness
 - Flu-like
 - Didn't feel like it
 - Didn't refill
 - Not sure of the benefits
 - Tired of injections
 - No one available to give
 - Dosing inconvenient
 - Pregnant or planning
 - Other

CONFIDENTIAL

The information contained herein may not be used, disclosed, or published without the written consent of Biogen MA Inc.

16.6. Treatment Adherence Questionnaire – Follow-up

Below are some questions regarding your use of Plegridy during the past 28 days. Please answer these questions as best as you can.

You can also seek help from a caregiver (anyone who usually provides care to you at home) to answer these questions.

1. During the past 28 days, did you take your recommended doses of Plegridy (125 mcg / every 14 days) in total? Yes No

2. If you answered “No” to question #1, how many injections did you not take during the past 28 days?

3. List all the reasons for not taking entire recommended dose. Please check the responses that apply.
 - Injection Anxiety
 - Skin Reaction
 - Forgot to take
 - Financial (I could not afford my medication)
 - Pain at injection site
 - Depression
 - Headache
 - Fatigue
 - Weakness
 - Flu-like
 - Didn't feel like it
 - Didn't refill
 - Not sure of the benefits
 - Tired of injections
 - No one available to give
 - Dosing inconvenient
 - Pregnant or planning
 - Other

CONFIDENTIAL

The information contained herein may not be used, disclosed, or published without the written consent of Biogen MA Inc.

16.7. Flu-Like Symptoms-Visual Analog Scale (FLS-VAS)

Since your last injection, how effective was the medication you took to reduce your flu-like symptoms

[figure not shown]
Not Effective ----- Very Effective
0 1 2 3 4 5 6 7 8 9 10

Since your last injection, how satisfied were you with the effectiveness of the medication you took to reduce your flu-like symptoms

Not Satisfied-----Very Satisfied
0 1 2 3 4 5 6 7 8 9 10

[figure not shown]
CONFIDENTIAL

The information contained herein may not be used, disclosed, or published without the written consent of Biogen MA Inc.

[figure not shown]
CONFIDENTIAL

The information contained herein may not be used, disclosed, or published without the written consent of
Biogen MA Inc.

[figure not shown]
CONFIDENTIAL

The information contained herein may not be used, disclosed, or published without the written consent of
Biogen MA Inc.

[figure not shown]
CONFIDENTIAL

The information contained herein may not be used, disclosed, or published without the written consent of
Biogen MA Inc.

[figure not shown]
CONFIDENTIAL

The information contained herein may not be used, disclosed, or published without the written consent of
Biogen MA Inc.

[figure not shown]
CONFIDENTIAL

The information contained herein may not be used, disclosed, or published without the written consent of
Biogen MA Inc.

[figure not shown]
CONFIDENTIAL

The information contained herein may not be used, disclosed, or published without the written consent of
Biogen MA Inc.

CONFIDENTIAL

The information contained herein may not be used, disclosed, or published without the written consent of
Biogen MA Inc.

CONFIDENTIAL

The information contained herein may not be used, disclosed, or published without the written consent of
Biogen MA Inc.

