8.1.2. Secondary Endpoints

Secondary endpoints will address non-serious AEs of special interest and other clinical effectiveness and non-safety related objectives as follows:

- Plegridy prescription and utilization patterns will be evaluated by assessment of prescribed dosing frequency, duration of Plegridy use, and primary reason for discontinuation of Plegridy (see Section 8.3.3 “MS Treatments and Concomitant Medications”).
- Effectiveness of Plegridy on specific MS clinical disease activity will be evaluated by assessment of relapse-related endpoints (e.g., ARR, time-to-first relapse, proportion of patients with relapse, and distribution of number of relapses and disability progression-related endpoints based on the EDSS (e.g., proportion of patients with progression and time-to-sustained progression for at least six months).

CONFIDENTIAL

The information contained herein may not be used, disclosed, or published without the written consent of Biogen MA Inc.

- Safety and tolerability of Plegridy will be assessed by the incidence proportion and incidence rates of non-serious AEs, including but not limited to FLS, ISRs, and AEs (including laboratory abnormalities) leading to treatment discontinuation.
- The impact of the severity of FLS on the ability to successfully manage symptoms via prophylaxis will be evaluated using the patient-reported FLS-VAS.
- Changes in FLS assessment and FLS-VAS over time.
- Changes in HRQoL measures will be evaluated over time using the EQ-5D-3L.
- Healthcare resource consumption will be evaluated by assessment of endpoints such as MS-related and non-MS-related physician visits, specialists' visits, use of physiotherapy, hospitalizations and lengths of stay, and emergency room (ER)/department visits.
- Patient-reported treatment adherence to Plegridy will be assessed using the Treatment Adherence Questionnaire for all patients.

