8.3.7. Patient-Reported and Health Economics Outcomes

Patient assessment of the following outcome measures will be collected, if consistent with local regulations:

- Impression of functional health and well-being using the EQ-5D-3L index score and the five individual component scores. Refer to Section 16.2, Appendix 1.
- FLS Assessment: Patients will assign a score from “0” to “3” to their muscle aches, chills, fatigue, and body temperature as follows: “0” for absent; “1” for mild, did not interfere with daily activities; “2” for moderate, sufficient to interfere with daily activities; and “3” for severe, bed rest required. Refer to Section 16.3, Appendix 2.

FLS-VAS: This patient-reported assessment includes two VAS ratings and will be performed to evaluate any prophylactic regimen such as acetaminophen, ibuprofen, aspirin, or naproxen used to alleviate FLS. The first VAS will assess the effectiveness of the prophylactic regimen used by the patient to control FLS. Patients will rate their prophylactic regimen to control FLS between “not effective” to “very effective”. The second VAS will evaluate the patient’s satisfaction with the effectiveness of the prescribed regimen to control FLS. Patients will rate their satisfaction from “not satisfied” to “very satisfied.” Refer to Section 16.7, Appendix 6.

Note: If a patient selects “Absent” for Question 1 of the FLS Assessment, then the FLS-VAS does not need to be completed for that patient.

- Healthcare resource consumption questionnaire: This patient-reported questionnaire will ask patients to report the frequency of MS-related, non-MS-related, relapse-related hospitalizations, MS-related neurological visits, MS-related ER visits, and visits to other health care professionals for MS-related and other reasons. Refer to Section 16.4, Appendix 3.
- Treatment adherence questionnaire: This is a patient-reported questionnaire that measures adherence to Plegridy treatment in the past 28 days, the number of missed injections, and reasons for discontinuation, if applicable. Refer to Section 16.5 and Section 16.6, Appendices 4 and 5.

Refer to Section 16.1 for the timing of assessments.

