Longitudinal evaluation of continuously measured secondary endpoints (e.g., EQ-5D-3L and FLS) may be performed using a linear regression model to evaluate the long term experience (e.g. change over time) of patients regarding these measures while on Plegridy. Categorical outcomes on healthcare resource consumption, treatment adherence, [REDACTED] and Plegridy prescription and utilization patterns will be summarized using frequencies and percentages. If necessary, a 95% CI based on binomial distribution might be provided for some of the categorical variables like patient adherence.

FLS-VAS includes the patients' ratings of effectiveness and satisfaction of controlling FLS with prophylactic regimens. The ratings will be summarized by mean (SD) and median (maximum and minimum). Changes of FLS-VAS ratings over time will also be summarized by mean (SD) and median (maximum and minimum). The changes of FLS-VAS ratings over time will be tested using a Wilcoxon rank-sum test. Longitudinal evaluation of FLS-VAS ratings using a linear regression model may be performed to evaluate patients' long-term experience (e.g., change over time) with the effectiveness and satisfaction of prophylactic regimens to control FLS while receiving Plegridy.

[REDACTED]

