16.3. FLU-LIKE SYMPTOMS (FLS) ASSESSMENT

Select the statement which best describes your MUSCLE ACHES, CHILLS and FATIGUE after your most recent injection.

- absent
- mild, did not interfere with daily activities
- moderate, interfered with daily activities
- severe, bed rest required

If you used any medication to reduce your Flu-Like Symptoms, please select the statement which best describes your MUSCLE ACHES, CHILLS and FATIGUE after taking the medication.

- absent
- mild, did not interfere with daily activities
- moderate, interfered with daily activities
- severe, bed rest required

If you experienced Flu-Like symptoms, did your symptoms last.

- 24 hours or less
- Greater than 24 hours

CONFIDENTIAL

The information contained herein may not be used, disclosed, or published without the written consent of
Biogen MA Inc.

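### The FLS-VAS items do not separate preventive from reactive medication and give no visible route for non-users, so the ratings cannot be reported as ratings of prophylaxis alone

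*Protocol*

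**What the plan says.** Four parts of the protocol give the FLS-VAS a prophylaxis meaning.

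- Section 7.3 sets a secondary objective on how patients rate prophylactic management.
- Section 8.1.2 turns it into an endpoint: "The impact of the severity of FLS on the ability to successfully manage symptoms via prophylaxis will be evaluated using the patient-reported FLS-VAS".
- Section 8.3.7 says of the instrument: "The first VAS will assess the effectiveness of the prophylactic regimen used by the patient to control FLS". The second scale is described as satisfaction with the same regimen.
- Section 8.6.5.4 carries this into the analysis: "FLS-VAS includes the patients' ratings of effectiveness and satisfaction of controlling FLS with prophylactic regimens". The ratings are summarized overall and over time, their change is tested, and a linear regression may follow.

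The form itself, in Section 16.7, has two items. The first reads "Since your last injection, how effective was the medication you took to reduce your flu-like symptoms", and the second asks "how satisfied were you with the effectiveness of the medication you took to reduce your flu-like symptoms". Each is answered on a line from 0 to 10.

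One completion rule is given, in Sections 8.3.2 and 8.3.7 and in a footnote to Table 4: a patient who answers 'Absent' to the first question of the FLS Assessment need not complete the FLS-VAS. The FLS Assessment in Section 16.3 also has an item that opens "If you used any medication to reduce your Flu-Like Symptoms", so that form does make an answer conditional on use.

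**The concern.** The label on the result and the question put to the patient differ in scope. A patient who takes a tablet only after chills begin can answer both items correctly, yet the rating would be tabulated as evidence about prophylaxis. The Abstract reports that treatment before and after injection is common in practice, so this is not a remote case.

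The second gap concerns patients who had FLS and took nothing. They are not covered by the one exemption, and the printed items presuppose a medicine. If some of them mark the line anyway, their marks rate no treatment at all.

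At stake is the reading of one secondary objective. Because change over time is tested, a shift in the mix of preventive users, reactive users and non-users could look like a change in how well prophylaxis works.

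**Working it through.** No sample size, power or error rate in the protocol depends on the FLS-VAS, so there is no stated figure to reproduce. The main check is a comparison of texts.

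**Step 1: construct against item.** Sections 7.3, 8.1.2, 8.3.7 and 8.6.5.4 name prophylaxis. Neither item in Section 16.7 mentions prevention, or timing relative to the injection or to symptom onset. Medicine taken preventively fits the items, and so does medicine taken reactively. The items therefore cover a wider construct that contains the intended one.

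**Step 2: can other data separate the two?** The conditional item in Section 16.3 identifies use of any medicine for FLS, but not when or why it was taken. Section 8.2.4.6 has all concomitant medication recorded. The fields listed in Section 8.3.3 are examples such as dose, frequency, dates and reason for stopping; indication and timing relative to injection are not among them. A split into preventive and reactive use is therefore not assured.

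**Step 3: non-users.** The only exemption is 'Absent' FLS, and no filter on medication use is stated for the summaries in Section 8.6.5.4. Section 8.6.5.2 says missing data will in general not be imputed, so a blank scale drops out and a marked scale stays in.

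**Step 4: illustration of size.** Let m be the mean rating among users, f the share of ratings that come from non-users, and s the score they give. Then

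reported mean = m(1 − f) + s·f, and the fall is f(m − s).

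The protocol gives none of these inputs; all are assumed.

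| m | f | Mean if s = 0 | Mean if s = 5 |
|---|---|---|---|
| 6 | 0.1 / 0.2 / 0.3 | 5.4 / 4.8 / 4.2 | 5.9 / 5.8 / 5.7 |
| 7 | 0.1 / 0.2 / 0.3 | 6.3 / 5.6 / 4.9 | 6.8 / 6.6 / 6.4 |
| 8 | 0.1 / 0.2 / 0.3 | 7.2 / 6.4 / 5.6 | 7.7 / 7.4 / 7.1 |

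The fall runs from 0.1 × (6 − 5) = 0.1 to 0.3 × (8 − 0) = 2.4 points. If non-users leave the scale blank, f = 0 and the fall is 0.

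**Step 5: change over time.** With m fixed at 7 and s = 0, a non-user share moving from 30% to 10% raises the reported mean from 4.9 to 6.3. That is 1.4 points with no change among users. Section 6.2.2 reports FLS incidence falling over the first six months of treatment, so a changing mix is plausible, but the protocol gives no data on it.

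**The case against.** The strongest reply is that the protocol uses the word prophylactic loosely. Section 8.3.7 says the instrument "will be performed to evaluate any prophylactic regimen such as acetaminophen, ibuprofen, aspirin, or naproxen used to alleviate FLS", which already blends prevention with relief. The opening words of the items may fix the period being rated rather than when the medicine was taken, and treatment after an injection can be scheduled rather than reactive. This stands as far as it goes. A reader might infer that the FLS-VAS measures something other than prophylaxis; the documents do not support that, because preventive use falls within the items.

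Second, no text tells non-users to rate. The rule exempts patients without FLS and is silent on the rest, and both the items and Section 8.3.7 presuppose a medicine in use. So it cannot be said that non-users are asked to complete the scale, only that nothing visible steers them away.

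Third, it is tempting to say the form has no box for patients who took nothing. Figures in Section 16.7 are not shown, and the electronic version is not available, so this can be said only of the text at hand.

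Fourth, the choice of which ratings enter a descriptive table is often left to the SAP. That is fair for the filter. It does not settle the mismatch between the items and the stated construct, since both are fixed in the protocol.

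**Conclusion.** The concern holds in a limited form. As written, the plan would report a mixed rating of medication for FLS under the name of prophylaxis, and any marks from non-users would be included. The first part follows from the wording alone, whatever the missing figures show. The second depends on what non-users do and on a form seen only in part.

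No size can be given from the documents. The range of 0 to 2.4 points rests wholly on assumed user means, non-user shares and scores, and the documents do not support quoting any single lowered mean as an expected bias. Nor do they show that a time trend will arise.

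This is one secondary patient-reported measure in a mainly descriptive study. No primary endpoint is touched. The correction is worth making because it is cheap and prevents an unsupported statement about a named objective.

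**What to change.** In Section 8.6.5.4, restrict the FLS-VAS summaries and change analyses to visits at which the conditional medication item of the FLS Assessment (Section 16.3) is answered. In Sections 7.3, 8.1.2, 8.3.7 and 8.6.5.4, name and interpret the result as patients' ratings of medication taken for FLS, covering its effectiveness and their satisfaction with it. Report a prophylaxis-only subset only if the concomitant-medication records actually show preventive use; do not promise that split in advance.

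The change uses data already collected and leaves the form as it is. Its costs are somewhat fewer ratings and a narrower claim. The filter is imperfect, since a non-user could answer the conditional item by mistake, and it does not separate preventive from reactive use. The relabelling deals with that second point.
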